### 3.4 Summary of Rationale

Based on these data, there are several reasons why the PETAL Network should conduct a trial of early vitamin D repletion to improve clinical outcomes in vitamin D deficient patients at high risk for ARDS and mortality:

1. Vitamin D deficiency is common in critically ill patients, and high dose supplementation can rapidly correct this deficiency.
2. Promising pre-clinical and epidemiological data strongly suggest potential clinical benefit and plausible mechanism for high-dose vitamin D supplementation to prevent ARDS and improve clinical outcomes.

3. Robust phase II trial data support the dosing regimen, safety, and potential clinical efficacy in ICU patients.
4. The trial leverages the PETAL infrastructure for early intervention prior to ICU admission, which is both feasible and desirable to optimize potential for clinical benefit.
5. The data collection requirements are modest to monitor safety and measure clinically relevant outcomes, which facilitate this large, simple, generalizable and cost-efficient trial that is consistent with NHLBI and PETAL Network goals.
6. Vitamin D is inexpensive, easy to administer, and safe, supporting the high potential to rapidly disseminate and change clinical practice if the trial results are positive.

## 3.5 Objectives

### 3.5.1 Primary Objective

To assess the efficacy and safety of early administration of vitamin D3 (cholecalciferol) in reducing mortality and morbidity for vitamin D deficient patients at high risk for ARDS and mortality.

### 3.5.2 Primary Hypothesis

Early administration of vitamin D3 (cholecalciferol) will improve all-cause, all-location mortality to day 90 in vitamin D deficient patients at high risk for ARDS and mortality.

## 3.6 Endpoints

### 3.6.1 Primary Endpoint

The primary endpoint is all-cause, all-location mortality to day 90. We will ascertain vital status at day 90 by chart review (for participants that remain in the hospital at day 90 or died in hospital prior to day 90). For participants that were discharged alive from the hospital prior to day 90, we will call the patient or proxy (e.g., research contact list and next-of-kin) on/after day 90 to determine vital status. For those that we are unable to verify vital status at day 90, we will use evidence from the medical record (e.g., healthcare visits after day 90), review of obituaries, or phone calls to healthcare facilities to determine that participants are alive. Finally, for participants that have missing 90-day mortality, we will use the Centers for Disease Control and Prevention's National Death Index (NDI) to determine vital status, using each patient's social security number (SSN) for an exact NDI match. At the time of final analysis, we will use best available mortality data and if vital status remains unknown (anticipated for <5%), will impute 90-day mortality based on last known location.

### 3.6.2 Secondary Endpoints

#### 3.6.2.1 Clinical Endpoints

1. **Study hospital length of stay among survivors to day 90:** Study hospital length of stay is defined as the number of days from enrollment (typically the day of hospital admission) to the day of study hospital discharge up to day 90. This endpoint will be analyzed only in survivors because hospital length of stay in those who die in the hospital is non-informative for this endpoint. In addition, we will use survivor average causal effect (SACE) methods to estimate hospital length of stay among participants that would have survived in both

treatment and control groups. Accordingly, these methods adjust for the impact of differential survival between treatment groups.

2. **Healthcare facility length of stay among survivors to day 90:** Healthcare facility length of stay is the time spent in another hospital or healthcare facility (e.g. long-term acute care [LTAC] hospitals or acute rehabilitation/skilled nursing facility), for the subgroup of participants that were discharged to another healthcare facility after the initial hospitalization. This measure is defined as the number of days from initial hospital discharge to the first facility discharge to home (pre-hospitalization level of care) up to day 90. Healthcare facility LOS is zero for patients discharged to home (pre-hospitalization level of care) from the study hospital. This endpoint will be analyzed only in survivors using SACE methods because healthcare facility length of stay in those who die during the follow-up period is non-informative for this endpoint.
3. **Alive and home at day 90:** This endpoint is the proportion of participants who have survived and are present at home, defined as pre-hospitalization level of care, at day 90.
4. **Ventilator free days (VFD) to day 28:** VFD depends on both duration of ventilation and mortality through study day 28. In participants who survive 28 days, VFD is defined as 28 minus duration of ventilation. Duration of ventilation is counted from the first study day of assisted breathing through the last day of assisted breathing provided the last day is prior to day 28. Otherwise, it is counted from the first study day of assisted breathing through day 28. For participants discharged with assisted ventilation (e.g., to LTAC facility) prior to day 28, a phone call will be required to assess ventilator status at day 28. Participants discharged prior to day 28 (but not to home) on unassisted breathing will be assumed to remain on unassisted breathing through day 28. Isolated periods of ventilation briefer than 24 hours for surgical procedures and ventilation solely for sleep disordered breathing do not count towards duration of ventilation. In participants who never require assisted breathing, duration of ventilation is zero. Participants who do not survive 28 days will be assigned zero VFD. VFD is undefined in participants with chronic/home mechanical ventilation (except solely for sleep disordered breathing) and they will be excluded from this analysis.
5. **Time to mortality to day 90:** Time to mortality will use best available data on vital status and date of death and censor based on last known alive date for participants with missing vital status.

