### 3.7 Subgroups

The primary analysis will be based on randomized participants with baseline 25OHD levels <20 ng/mL by LC/MS/MS (confirmed vitamin D deficient cohort). Secondary analysis will be based on the screened vitamin D deficient cohort (all randomized patients). *A priori* subgroups for analysis will include age, sex, race/ethnicity, residence (independent vs. long-term care facility), BMI, pre-hospitalization vitamin D supplementation, baseline 25OHD level (by the LC/MS/MS method), baseline renal function, ARDS risk factor (e.g., infectious vs non-infectious), LIPS score, pre-randomization mechanical ventilation status, pre-randomization presence of ARDS, and source of ICU admission.

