### Pulmonary

- a) Pneumonia
- b) Aspiration
- c) Smoke Inhalation
- d) Lung contusion
- e) Mechanical ventilation for acute hypoxemic or hypercarbic respiratory failure

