## 6 DATA VARIABLES AND SPECIMENS

### 6.1 Background Assessments

1. Inclusion/exclusion criteria
2. Demographic and admission data (including age, sex, race/ethnicity, pre-hospitalization level of care)
3. Pertinent medical history (including Charlson co-morbidity score, renal function, chronic ventilation)
4. Height; measured body weight (MBW); calculated predicted body weight (PBW); body mass index (BMI)
5. Ventilator status prior to randomization
6. Location when inclusion criteria met
  - ED, ward, operation room, referring hospital
7. ICU Admission Service
  - Medical
  - Surgical scheduled
  - Surgical unscheduled
  - Trauma
  - Other

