3.3 Secondary Endpoints

3.3.1 Clinical Endpoints

Hospital mortality to day 90, and alive and home (prior level of care) at day 90, and 28 day mortality will be compared between treatment groups using Pearson's chi-square test.

Hospital length of stay and healthcare facility length of stay will be analyzed only in survivors to day 90. We will use survivor average causal effect (SACE) methods to estimate each outcome among participants that would have survived in both treatment and control groups⁴. The SACE methodology includes a model for predicting survival using baseline covariates. The covariates used will be sex, age, Charlson, SOFA, baseline 25OHD as measured by LCMS, and race/ethnicity (non-Hispanic white versus other).

Ventilator-free days to day 28 will be compared between treatment groups using a t-test.

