3.3.2 Physiological Endpoints

Binary endpoints will be compared between treatment groups using Pearson's chi-square test.

Ordinal endpoints will be scored as 1,2,3, ... and compared between treatment groups using the CMH mean score test.

Continuous endpoints will be compared between treatment groups using a t-test with two exceptions. The highest creatinine and CV SOFA score will be analyzed controlling for baseline value using repeated measures ANOVA with a treatment by time interaction and shared intercept at time 0 (baseline). This model is equivalent to ANCOVA controlling for baseline but is able to make use of all available data.

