3.3.5 Figures

A log-rank test will be used to compare the time to 90 day mortality in the two treatment groups.

A quadratic smoothing spline in each treatment group will be used to display the relationship between the primary mortality outcome and baseline 25OHD level as measured by LCMS. Pointwise bootstrap confidence intervals for the difference between the two curves will be calculated at LCMS values of 5, 10, 15, 20, 25, and 30.

4. Supplementary Materials Outline and Statistical Methods

The supplementary materials will include the following tables and figures.

Table. Baseline Characteristics for confirmed not deficient (LCMS \geq 20), confirmed deficient, and screened deficient (all randomized)

- Demographics
- Co-Morbidities—Charlson, BMI, eGFR, pre-hospital level of care
- VIOLET Risk Factors
- Location—intent to admit, ICU destination
- Illness Severity—SOFA, LIPS, mechanical ventilation, ARDS, vasopressor use, vital signs, WBC, lactate
- Baseline vitamin D (home meds, vitD level, calcium level)

Table. Study Initiation/Dosing for confirmed deficient and screened deficient (all randomized)

- Inclusion to Randomization (time)
- Randomization to Drug Administration (time)
- Study Drug Dosing
- Study Drug Tolerance

Figure. Subgroup Analysis of Primary Endpoint (confirmed deficient)

- Age: <60, ≥60
- Sex: M, F
- Race/ethnicity: NH white, NH black, Hispanic, other
- Residence: independent, long-term care facility
- BMI: <20, 20-24.9, 25-29.9, 30-34.9, ≥35
- Pre-hospitalization vitamin D supplementation: none, 1-800 IU/day, >800 IU/day
- Baseline 25OHD level (by the LCMS): <12, 12-19, 20-29, ≥30 AND <10, 10-19, 20-29, ≥30 AND <20, ≥20
- Baseline renal function: eGFR 15 (or on dialysis), 15-29, 30-59, 60-89, ≥90
- ARDS risk factor: sepsis, pneumonia, shock, mechanical ventilation, other AND infectious, non-infectious
- LIPS score: <4, ≥4
- Pre-randomization mechanical ventilation status: Y, N
- Pre-randomization presence of ARDS: Y, N
- Source of ICU admission: ED, other
- ICU destination: MICU, other
- Modified intention to treat (received full study drug dose without vomiting within 1 hour): yes, no

Figure. Subgroup Analysis of Primary Endpoint for screened deficient (all randomized)

- Age: <60, ≥60
- Sex: M, F
- Race/ethnicity: NH white, NH black, Hispanic, other
- Residence: independent, long-term care facility
- BMI: <20, 20-24.9, 25-29.9, 30-34.9, ≥35
- Pre-hospitalization vitamin D supplementation: none, 1-800 IU/day, >800 IU/day

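### Ventilator-free days are compared by an unadjusted t-test although pre-randomization ventilator status is already collected; adding it would gain precision at no data cost, by an amount the documents do not fix

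*Protocol*

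**What the plan says.** **The endpoint.** Protocol 3.6.2.1 item 4 (repeated in SAP 2.10.2) subtracts the time spent ventilated from 28 to give VFD in survivors to day 28, under this counting rule: "Duration of ventilation is counted from the first study day of assisted breathing through the last day of assisted breathing". Survivors who never need assisted breathing have duration zero, so they score 28. For deaths, "Participants who do not survive 28 days will be assigned zero VFD".

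**The test.** SAP 3.3.1: "Ventilator-free days to day 28 will be compared between treatment groups using a t-test". No covariate is named.

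**The population.** One of the eight qualifying risk factors is "Mechanical ventilation for acute hypoxemic or hypercarbic respiratory failure" (Protocol 2.5 and 4.2). The trial therefore mixes participants who are ventilated at entry with participants who are not.

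**The covariate.** Protocol 6.1 item 5 collects "Ventilator status prior to randomization", and the schedule in Appendix A marks ventilator status as required on day 0. Protocol 3.7 lists it among the a priori subgroups: "pre-randomization mechanical ventilation status, pre-randomization presence of ARDS, and source of ICU admission". SAP Section 4 codes it "Pre-randomization mechanical ventilation status: Y, N", but only for the subgroup figures of the mortality endpoint. Protocol 4.6 stratifies randomization by hospital only.

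**Related text.** Under VFD, the SAP Section 3 table asks for the proportion ventilated as an aid to interpretation. For two other endpoints, SAP 3.3.2 adjusts: "The highest creatinine and CV SOFA score will be analyzed controlling for baseline value".

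**The concern.** The scoring separates two kinds of participant. Someone ventilated at entry begins to lose days at study day 0. Someone not ventilated at entry scores 28 unless they die by day 28 or need ventilation later. The difference between these groups is known before treatment starts, but in an unadjusted t-test it stays in the error term. Stratification does not remove it either.

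The plan shows awareness of the issue. Protocol 4.3.1 justifies exclusion criterion 8 partly because some ventilated patients would confound interpretation of endpoints such as VFD, and the SAP asks for the proportion ventilated to be shown beside the result. Neither step narrows the confidence interval. What is at stake is the width of that interval, and hence the power, for one secondary endpoint.

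**Working it through.** **The plan's own figure.** There is none for VFD: no standard deviation, effect size or power. The stated 87.4% power concerns mortality and is not affected.

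**Inputs.** From the documents: the scoring rule, 1:1 allocation, and 2400 participants in the confirmed deficient cohort (1200 per arm). Not in the documents, so assumed: the share p ventilated at entry and, for each entry group j (1 = ventilated, 0 = not), 28-day mortality d, survivor mean VFD m and survivor SD s.

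**Formulas.** Counting deaths as zero:

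- Group mean: μj = (1 − dj) × mj
- Group variance: vj = (1 − dj)(sj² + mj²) − μj²
- Between-group part: B = p(1 − p)(μ1 − μ0)²
- Within-group part: W = p·v1 + (1 − p)·v0
- Share of VFD variance explained by entry status: R² = B / (B + W)

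Adjusting for entry status multiplies the variance of the treatment comparison by about (1 − R²).

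**Worked case.** Take p = 0.30; ventilated m = 20, s = 7, d = 0.20; not ventilated m = 27, s = 3, d = 0.12.

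- μ1 = 0.80 × 20 = 16.0; μ0 = 0.88 × 27 = 23.76
- v1 = 0.80 × (49 + 400) − 256 = 103.2; v0 = 0.88 × (9 + 729) − 564.5 = 84.9
- W = 0.30 × 103.2 + 0.70 × 84.9 = 90.4; B = 0.21 × 7.76² = 12.6
- R² = 12.6 / 103.0 = 12.3%; total SD = 10.2

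**Weaker case.** With p = 0.30, survivor means 22 and 26 (SD 6 and 4) and mortality 20% and 15%: B = 0.21 × 4.5² = 4.25, W = 101.7, R² = 4.0%.

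**Range.** Two sets of assumptions were run.

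- A broad grid of 160 scenarios: p from 20% to 50%; survivor means 18 to 24 (ventilated) and 26 to 27 (not); mortality 15–30% and 10–15%. R² ran from 0.4% to 26.9%, with median 9.9% and 10th to 90th percentile 2.8% to 20.1%. In 26% of scenarios it was below 6%.
- A narrower grid of 36 scenarios: p from 25% to 50%; mean VFD 18 to 21 (SD 7) in ventilated survivors; mortality 18–28% and 9–13%; 10–20% ventilated later. R² ran from 6.3% to 28.4%.

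Together: roughly 0% to 28%, typically about 10%.

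**What that means.** The SE ratio is √(1 − R²) and the equivalent sample size is 1/(1 − R²). With an assumed SD of 10.2, SE = 10.2 × √((2/1200)(1 − R²)). Power is for an assumed true difference of 1.0 day, two-sided 5%.

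| R² | SE ratio | Equivalent extra participants | SE (days) | Power |
|---|---|---|---|---|
| 0 (t-test) | 1 | – | 0.416 | 67% |
| 0.4% | 0.998 | 0.4% | 0.416 | 67% |
| 10% | 0.949 | 11% | 0.395 | 72% |
| 28% | 0.849 | 39% | 0.353 | 81% |

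At R² = 10%, the gain equals about 0.111 × 2400 = 267 extra participants for this endpoint.

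**Validity.** In simulated null trials of 2400 participants, the t-test rejected 4.7% of the time and the adjusted model with robust standard errors 5.0%.

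**The case against.** The strongest reply is that nothing here is an error. Under randomization the t-test is unbiased and keeps its type I error. VFD is one of many secondary endpoints, tested without multiplicity control (SAP 3.1). Unadjusted testing is also the SAP's general approach: the primary mortality model has no covariates and the binary endpoints use chi-square tests. The SAP partly deals with the mixed population in its reporting: mechanical ventilation is in the baseline table, the proportion ventilated stands beside VFD, and new mechanical ventilation to day 7 is a separate endpoint. Finally, the gain may be small. Qualifying ventilation includes non-invasive support (Protocol 4.2.2), where short courses are plausible, and short courses bring the two groups closer together.

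All of this stands. It limits the point to an optional gain in precision, but gives no reason to forgo that gain: with over 2000 participants, one binary covariate costs almost nothing even if it explains little.

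A reader might also infer a contradiction within the SAP, because creatinine and CV SOFA are controlled for baseline and VFD is not. The documents do not support that. Those two outcomes are measured on the same scale at baseline and follow-up, and SAP 3.3.2 presents them as exceptions to its t-test rule. VFD is a 28-day composite with no baseline measurement; entry ventilator status is a prognostic factor, not the endpoint's own baseline value. The comparison shows only that the SAP accepts baseline terms where they help.

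**Conclusion.** The point holds as a loss of precision in a valid secondary analysis. SAP 3.3.1 leaves out a predictor that is already collected, already coded and not controlled by stratification. The estimate of about 10% of variance, within roughly 0% to 28%, rests entirely on assumed ventilation shares, mortality and survivor VFD by entry status. The SE and power in days also assume an SD of 10.2 and a 1.0-day effect.

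Three stronger readings should be resisted:

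- **That at least 6% of variance is certain to be recovered.** That figure is the lower edge of one set of assumptions, and about a quarter of the broader scenarios fall below it.
- **That chance imbalance in entry ventilation is a second harm.** It is already part of the t-test's standard error, so counting it again would count the same loss twice.
- **That VFD is the trial's main ventilation endpoint, or that a stated trial figure changes.** The documents give VFD no such rank, and neither the 87.4% power nor the mortality analysis is touched.

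**What to change.** In SAP 3.3.1, replace the VFD t-test sentence with wording such as:

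*VFD to day 28 will be compared using a linear model with terms for treatment and pre-randomization mechanical ventilation status (Y/N), with robust standard errors. The adjusted difference in means and its 95% confidence interval will be reported. Unadjusted means by arm will be shown for description.*

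Y/N is the coding the SAP already uses. Protocol 6.1 item 5 does not itself specify a split into invasive and non-invasive support, so the change should not depend on one. SAP 4.1 would carry the same method to the screened deficient cohort.

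The cost is one sentence. The endpoint, its scoring and the target are unchanged, and no new data are needed. The wording should be fixed before unblinding, because a covariate added afterwards would look data-driven.

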### 3.6.2.2 Physiological Endpoints

6. **Development and severity of ARDS to day 7:** We will determine the presence and severity of ARDS for each day of mechanical ventilation to day 7 using the following approach:
  - a. For each ventilator day: if ABG available between 2:00 AM and 8:00 AM, measure P/F (PaO2, FiO2 and PEEP) for all ABGs during this time window daily to day 7. Or, for ventilator days that no ABG available between 2:00 AM and 8:00 AM, determine lowest imputed P/F from measured S/F (SpO2, FiO2, and PEEP). See Appendix B for P/F imputation table.
  - b. For participants with P/F <300 or imputed P/F <300, FiO2 ≥40%, and PEEP ≥5 cm H2O, determine if hypoxemia is valid, acute, and not fully explained by CHF or fluid overload
  - c. If yes to item (b), local investigators will:

- i. Review the first CXR (or CT) performed on each ventilated day with valid P/F or imputed P/F <300 (to day 7). If no chest imaging studies are present that day, site investigators may review imaging one day before or after to determine if ARDS imaging criteria met.
  - ii. Assess if the images are consistent with ARDS (bilateral opacities not fully explained by effusions, lobar/lung collapse, or nodules). If equivocal, the reviewing investigator will adjudicate with additional investigators.
7. **Change in organ failure severity to day 7:** We will measure acute organ failure severity daily to day 7 for three key organ systems: acute hypoxemic respiratory failure, acute kidney injury, and cardiovascular failure (i.e., shock). We will measure acute hypoxemic respiratory failure using data from the ARDS assessment, except this outcome does not require chest imaging consistent with ARDS. We will measure acute kidney injury by highest daily creatinine values or new use of dialysis/ renal replacement therapy (chronic dialysis participants are excluded). We will measure cardiovascular failure by highest daily dose of vasopressors (epinephrine, norepinephrine, dopamine, phenylephrine, or vasopressin).
8. **Plasma 25OHD levels:** In addition to the screening vitamin D test (for trial entry), we will measure gold-standard plasma 25OHD levels at baseline for all randomized participants and at day 3 in the first 300 randomized participants to confirm biomarker response to the intervention. The gold-standard test will be done in batch using LC/MS/MS methods. Individual results will not be available to investigators and coordinators to avoid unblinding. Based on pre-specified rules and in consultation with the DSMB (who will have access to additional adverse event data), we may require changes to the vitamin D dose or extend the duration of 25OHD/calcium monitoring.
9. **Plasma IL-6 levels:** We will measure plasma IL-6 levels at baseline and day 3 in the first 300 randomized participants in batch concurrent with 25OHD testing. IL-6 is a pro-inflammatory cytokine associated with increased incidence and severity of ARDS severity and worse clinical outcomes. Vitamin D may improve outcomes in critically ill patients by reducing levels of IL-6 (either causal association or as a result of improved recovery).

### 3.6.2.3 Safety Endpoints

10. **Calcium levels to day 14:** Because the half-life of 25OHD is approximately 2 weeks, we will record clinically available serum or ionized calcium levels through day 14 for all randomized participants. In addition, we will measure baseline and day 3 in the first 300 randomized participants in real time, either as part of routine clinical care or as a research procedure if not available. Day 3 is the when 25OHD levels peak in ICU patients given 540,000 IU of vitamin D. While no prior study of acute vitamin D repletion, using similar high doses as our trial, has observed clinically important hypercalcemia, we will confirm these findings in the VIOLET trial. Because little change in calcium levels is anticipated, access to individual-level calcium results will not unblind study staff. During the trial, the DSMB may seek additional subject measurements for safety assessment, though this is not anticipated.
11. **Kidney stones to day 90:** While an association between hypervitaminosis D and kidney stones has been suggested, the relationship with high dose vitamin D supplementation and kidney stones remains controversial. We will assess for incident kidney stones by chart

review at the end of the hospitalization and by self-report at the 90 day phone call for those discharged from the hospital prior to day 90.

12. **Fall-related fractures to day 90:** The association between acute vitamin D supplementation and falls/fractures remains unclear. Most data suggest that high dose vitamin D in healthy outpatients may improve muscle function, balance, and bone mineral density, and thus decrease fall-related fractures, but other data suggest that high dose vitamin D supplementation may actually increase the incidence of falls/fractures. Because of this uncertainty and limited data in hospitalized patients, we will assess for incident fall-related fractures by chart review at the end of the hospitalization and by self-report at the 90 day phone call for those discharged from the hospital prior to day 90.

